Appendix A Schedule of Study Procedures (continued)

	Screening Visit 1	Base-line Visit 2	Random-ization Visit 3	Double-Blind Treatment Repeated yearly				Unscheduled - CMFV (q) (v)	EoS / EW Visit (b) (j)	Follow-up Visit (c)
				3 (a)	6	9 (a)	12			
Study Month:	-4	-1	0 (Day 0)	3 (a)	6	9 (a)	12			EoS/EW+0.5
Visit Window (t):	Max Day -125	Max Day -35		±2 weeks	±2 weeks	±2 weeks	±2 weeks	Within approx. 30 days of trigger		
Efficacy (continued)										
GDS		X			X		X		X(u)	
ADCS-MCFSI		X			X		X		X(u)	
EQ-5D		X						X	X(u)	
SF-36		X						X	X(u)	
IQCODE		X			X		X		X(u)	
ADCS ADL-PI		X			X		X		X(u)	
NPI-Q		X						X	X(u)	
ADCS-RUI		X			X		X	X	X(u)	
CDR		X						X	X(u)	
ADCS-CGIC- MCI		X			X		X	X (u)	X(u)	

Footnotes are on the following page.

Excl=exclusion, Incl=inclusion.

- (a) Telephone contact (should be every 3 months between the semi-annual clinic visits for the life of the study).
- (b) EoS/EW Visit is an ad hoc visit that, for study completion, would take place as soon as possible after a regularly scheduled Study Visit, either after the CIAC has confirmed that the subject has reached the MCI due to AD primary endpoint event (or any other irreversible cognitive impairment or dementia) or after a subject has withdrawn prematurely from the study. In cases where the endpoint has been reached, the efficacy assessments will not need to be captured at this Visit.
- (c) Subjects will have a safety follow-up call 2 weeks after completion or withdrawal. Subjects who withdraw their consent should still be contacted for a safety follow-up call, but the contact should only be recorded in the medical records (and not in the [e]CRF), according to data protection regulations.
- (d) footnote deleted
- (e) Please refer to Section 10.2.1.3.
- (f) As part of the comprehensive medical follow-up evaluation to rule out other causes of dementia and confirm the clinical diagnosis of MCI due to AD (See section 6.2.4). An MRI scan is not required to be performed if a study related MRI scan was collected within 6 months of the CMFV. For subjects who have contraindications for the MRI procedure (such as unremovable ferromagnetic dental work, cardiac pacemakers, etc) a CT scan can be done instead.
- (g) DNA sample expected to be collected at this visit, but if necessary, may be collected at any visit after randomization.
- (h) Sites should make every attempt complete the cognitive test battery in the order of outlined in Section 9.1.17.

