- (i) Cognitive Battery is completed at an Unscheduled Visit or EoS/EW Visit if the visit occurs greater than 3 months after the previous regularly scheduled visit.
- (j) Subjects who discontinue study medication prematurely should be contacted by the study site every 6 months until the conclusion of the study via telephone to assess the general well being of the subject as well as to obtain any changes in medications related to cognitive health. In the event the subject is not able to be reached, the subject's project partner or primary care physician can be contacted to obtain this information.
- (k) female subjects only.
- (l) Family history is captured at the first 6 month visit during year 1 of the study.
- (m) Please refer to Table 9.a and lab manual for detailed test schedule.
- (n) RNA sample to be collected at Day 0, Month 12 of Year 1, Year 2, Year 3, Year 4 and EoS.
- (o) Greater detail is given below. Note: If subject has been off drug for 3 or more days prior to Unscheduled CMFV, or EoS/EW Visit, the PK samples should not be collected.
- (p) A subject's age will be collected at these post-Baseline study Visits only in countries that do not allow collection of a subject's date of birth.
- (q) Procedures for Unscheduled visits for CMFV includes the assessments marked, and should only be conducted after appropriate criteria are met as described in Section 6.2.4. Unscheduled visits for other concerns, including safety, the investigator is expected to conduct whatever assessments are necessary.
- (r) If sites prefer to split the ICF process at Visit 1 and Visit 2 into a screening informed consent and study entry informed consent and have IEC/RIB approval to do so, this is permitted.
- (s) ADCS-RUI should be administered every 6 months.
- (t) Visit Window also applies to Project Partner assessments.
- (u) These assessments only need to be administered at the applicable visit if it occurs greater than 3 months from the last administration of the particular assessment.
- (v) At the Investigator's discretion, CMFV assessments may be conducted at the routine Month 6 or Month 12 Visit in situations where the CMFV conducted as an outcome of the previous scheduled office visit resulted in an MCI due to AD diagnosis. Refer to Section 6.2.4 for further detail.

CONFIDENTIAL

Schedule for Pharmacokinetic Sample Collection

Group	Dosing Time (approximate)	Sample Collection(a)			
		Pre-Dose	Sample Collection Time Post-Dose		

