9.1.3 Definition of Study Day and Study Visit Windows

A windowing convention will be used to determine the analysis value for a given study visit that applies to observed data.

Study Day -1 corresponds to the randomization date. Other study days are defined relative to Study Day 1, the date of first double-blind study drug dose. Relative day is calculated as (date of interest - date of first dose +1) for study days on or after the date of first dose and as (date of interest - date of first dose) for study days prior to the first dose date.

For each visit, a window will be defined such that the lower and upper bounds of each window is generally the midpoint between 2 consecutive study visits. The visit windows and applicable study day ranges are presented below in [Table 9.a](#).

Table 9.a Visit Windows

Nominal Visit Month	Nominal Visit Day	vMRI	Height, ECG, Chemistry and Hematology, PK, RU, DNA/RNA, PE	All Other Variables (c)
Baseline	-36 to -1 (a)	≤ -1	≤ -1 (b)	≤ -1
6	183			2—273
12	365		2—547	274—456
18	548			457—638
24	731	639—821	548—912	639—821
30	913			822—1003
36	1096		913—1277	1004—1186
42	1278			1187—1369
48	1461		1278—1643	1370—1551
54	1644			1552—1734
60	1826		1644—1917	1735—1917
66/Final (d)	2009	≥1370	≥1918	≥1918

(a) Consistent with SDTM dataset standards, date of first dose of double-blind study drug is defined as Day 1, and the day before is defined as Day -1. Per the protocol, date of first dose of dose of double-blind study drug is scheduled for the day after randomization. Exemptions were granted on a case-by-case basis for subjects who had a screening-to-randomization time frame greater than the 35-day window planned per the protocol.

(b) No baseline assessment for PK samples.

(c) CDR and NPI-Q are collected only at Baseline (Visit 2), unscheduled visits (eg, comprehensive medical follow-up visits) and End of Study / Early Withdrawal.

(d) The planned study duration of 5.5 years is approximate, since this is an event-driven trial.

For safety variables, visit windows are exhaustive and the lower and upper bounds of each window are the midpoints between the scheduled visit days for the current visit and the adjacent visits.

More than 1 result for a parameter may be obtained in a visit window. In such an event, the result with the date closest to the scheduled visit day will be used. In the event of 2 observations equidistant to the scheduled visit day, the later of the observations will be used.

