The change from baseline variables for the CVLT-II test (CVLT_T1, CVLT_T2, CVLT_T3, CVLT_T4, CVLT_T5, CVLT_TOT, CVLT_TB, CVLTSDEL, CVLTLDEL, CVLTINTR, CVLT_REP, CVLTHITS, and CVLT_FP) will each be analyzed as a continuous variable by study visit using an MMRM model similar to the ones described above for the key secondary variables.

The change from baseline variables for the cognitive battery domain scores (memory, executive function, language, and attention) will each be analyzed as a continuous variable by study visit using an MMRM model similar to the ones described above for the key secondary variables.

The change from baseline variables for GDS Total score, ADCS MCFSI total score, IQCODE Overall mean score, and ADCS ADL-PI Physical Function total score will each be analyzed as a continuous variable by study visit using an MMRM model similar to the ones described above for the key secondary variables.

The ADCS-CGIC-MCI total, cognition, behavior, and functional ability scores will each be analyzed as continuous variables by study visit using a MMRM models similar to the ones described above for the key secondary variables (using the appropriate corresponding ADCS-CGIC-MCI baseline score). In addition, each of these 4 ADCS-CGIC-MCI variables will be analyzed at the last visit using the Cochran-Mantel-Haenszel test and stratifying by center.

The MMSE total score is scheduled to be collected at 6-month visits and EoS/EW. Summary statistics will be used to present MMSE total score and change from baseline in MMSE total score at EoS/EW.

The CDR and NPI-Q are scheduled to be collected at baseline and EoS/EW. The CDR Global Score and domain scores will be presented using shift tables from baseline to EoS/EW. Summary statistics will be used to present CDR-SB and change from baseline in CDR-SB at EoS/EW. In addition, each of the 6 CDR domain scores at Baseline and at each time point when MCI due to AD was diagnosed will be included in the listings.

For each of the NPI-Q variables Total Severity Score and Caregiver Distress Score, the change from baseline in NPI-Q from baseline to EoS/EW will be analyzed using an ANCOVA model analogous to the model for the key secondary endpoints. The following SAS code will be used for the ANCOVA analysis:

- Proc mixed data=all;
- class treat center gender;

- model Change = Baseline treat center gender education age;
- lsmeans treat / cl pdiff;

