MRIs will be done as part of the comprehensive medical follow-up evaluation to rule out other causes of dementia and confirm the clinical diagnosis of MCI due to AD (see Section 6.2.4 of the protocol). For subjects who have contraindications for the MRI procedure (such as unremovable ferromagnetic dental work, cardiac pacemakers, etc) a CT scan can be done instead. The possible categories for the interpretation results are: Within Normal Limits; Abnormal, Not Clinically Significant; and Abnormal, Clinically Significant. The last available MRI/CT scan interpretation results for each subject will be summarized by treatment group, and all MRI/CT scan interpretation results will be presented in the listings.

Except for time-to-event analyses and the summary of MRI interpretation results, unscheduled visit values will be excluded from the summaries and analyses but will be included in the end-of-text CSR listings.

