9.13 Other Outcomes

The change from baseline variables for the EQ-5D index utility score and VAS scores, SF-36 Physical Component and Mental Component summary T scores, and the 8 SF-36 domain T scores will each be analyzed as a continuous variable by study visit using an MMRM model similar to the ones described above for the key secondary variables. (The Physical Component and Mental Component summary scores and reliability consistency index scores will be included in the derived datasets, but analyses for these variables will not be presented in the CSR; they may be provided in the future in a separate report.)

For the following endpoints (corresponding to the analysis method for the key secondary endpoints), subgroup/responder analyses by MCI event status (ie, subject had confirmed a MCI due to AD event during the study, subject did not have confirmed MCI due to AD event during the study) will be done (using the corresponding measurements at the time of the MCI due to AD

event or using the last non-missing measurements for subject who did not have an MCI due to AD event during the study:

- Change in HRQoL (European Quality of life scale [Euro-Qol EQ-5D] health utility and VAS scores, and Short Form-36 [SF-36] Mental and Physical component scores).

Responder analyses involve subgroups which are defined using post-baseline data and so need to be interpreted cautiously. Analysis results for subgroups containing less than 20% of the total subjects in the primary efficacy analysis population should be interpreted especially cautiously. The treatment groups will be compared within each subgroup. Additional exploratory analyses examining subgroup effect and treatment-by-subgroup interaction may be performed.

Data will be collected to allow evaluation of the impact of pioglitazone on health care resource utilization (RU) in individuals at high risk of developing MCI due to AD, to be used in future pharmacoeconomic evaluation of pioglitazone. (These analyses will not be presented in the CSR, but may be provided in the future in a separate report.)

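### The final CDR and NPI-Q analyses in SAP 9.9.9 can omit many confirmed converters: they use only EoS/EW values, which converters need not provide, and exclude the follow-up visit values that converters do have

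*SAP*

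**What the plan says.** **Collection.** SAP Table 9.a, footnote (c): "CDR and NPI-Q are collected only at Baseline (Visit 2), unscheduled visits (eg, comprehensive medical follow-up visits) and End of Study / Early Withdrawal". Protocol Table 9.c gives EQ-5D and SF-36 the same pattern, with no routine 6-month collection.

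**Waivers at EoS/EW.** Protocol Appendix A lists all four instruments under efficacy. Footnote (b) says of the EoS/EW visit: "In cases where the endpoint has been reached, the efficacy assessments will not need to be captured at this Visit". Footnote (u), attached to all four at EoS/EW, says: "These assessments only need to be administered at the applicable visit if it occurs greater than 3 months from the last administration".

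**Final analysis, SAP 9.9.9.**
- CDR: "The CDR Global Score and domain scores will be presented using shift tables from baseline to EoS/EW".
- CDR-SB: "Summary statistics will be used to present CDR-SB and change from baseline in CDR-SB at EoS/EW".
- NPI-Q: "the change from baseline in NPI-Q from baseline to EoS/EW will be analyzed using an ANCOVA model".
- CDR domain scores at each diagnosis go to the listings only.
- The section closes with the general exclusion: "Except for time-to-event analyses and the summary of MRI interpretation results, unscheduled visit values will be excluded from the summaries and analyses".

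**Quality of life, SAP 9.13.** EQ-5D and SF-36 scores "will each be analyzed as a continuous variable by study visit using an MMRM model similar to the ones described above". A second analysis splits subjects by MCI event status. It takes converters' values at the time of the event and other subjects' last non-missing values.

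**The concern.** Each rule is reasonable alone. Together they discard values that the trial already holds. A subject on the way to a confirmed event has CDR and NPI-Q at the CMFVs, is confirmed by the adjudication committee, and then attends an EoS visit where the instruments need not be repeated. The analysis looks only at EoS/EW and drops the CMFV values. No rule in SAP 9.9.9 carries a CMFV value into the EoS/EW position. Under footnote (u) the EoS assessment is skipped because a recent value exists, and the SAP then excludes that value.

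The missingness is selected on the outcome. A table meant to show movement on CDR could leave out subjects whom the trial itself has confirmed as having moved. If the arms differ in conversion, they also differ in how many subjects are left out.

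**Working it through.** **1. Following a confirmed converter through the rules.**
- Protocol 6.2.4: a trigger leads to a CMFV with CDR and NPI-Q. After a second consecutive CMFV the case goes to adjudication. A confirmed subject is withdrawn as a completer and scheduled for EoS.
- Appendix A footnote (b): efficacy assessments are not required at that EoS visit.
- SAP 9.9.9: the analysis needs an EoS/EW value and excludes unscheduled values.
- Result: if the site does not collect them at EoS, the subject has no post-baseline CDR or NPI-Q value in the analysis.

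Holding the second CMFV at a routine visit (Protocol 6.2.4; Appendix A footnote v) does not help, because the CDR and NPI-Q analyses still take EoS/EW alone. The futility package assigns CDR-SB to visit windows (SAP 9.16); the final analysis has no such rule.

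**2. Consequence for CDR.** Protocol Table 4.b requires CDR 0.5 for MCI due to AD, and entry requires CDR 0. Each MCI converter without an EoS/EW value is therefore a 0-to-0.5 shift missing from the table.

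**3. Size.** Inputs (Protocol 13.3; SAP 8.0): 5-year event rates 15% and 9%, dropout 12% per year, two-sided alpha 0.01, power 90%, 202 events, 1,173 per arm required. Protocol 6.1 expects 1,470 per arm.

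The plan's figure first. With exponential times, HR = ln(0.91)/ln(0.85) = 0.580. Schoenfeld events = 4 × (2.576 + 1.282)² / (ln 0.580)² = 201, against 202 stated, so it reproduces.

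Split of the 202 events by arm:
- Hazards per year: placebo −ln(0.85)/5 = 0.0325; pioglitazone −ln(0.91)/5 = 0.0189; dropout d = −ln(0.88) = 0.1278.
- Probability of an observed event by 5 years = λ/(λ+d) × [1 − exp(−5(λ+d))]: placebo 0.112, pioglitazone 0.067.
- Split before rounding: 126.4 placebo and 75.6 pioglitazone, approximately 202 × 0.112/0.179 and 202 × 0.067/0.179.
- Assuming 4 or 6 years of common follow-up instead gives 126.7/75.3 or 126.2/75.8, so the split hardly depends on duration.

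| Randomized per arm | Placebo | Pioglitazone |
|---|---|---|
| 1,470 | 126.4/1,470 = 8.6% | 75.6/1,470 = 5.1% |
| 1,173 | 126.4/1,173 = 10.8% | 75.6/1,173 = 6.4% |

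(Rounding to 76 before dividing by 1,470 gives 5.2%.)

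**4. Range.** These are ceilings: they assume that no converter has an EoS/EW value. The documents give no capture rate. If a fraction q of converters is assessed at EoS anyway, the missing numbers are 126.4(1−q) and 75.6(1−q): 126 and 76 at q = 0, 63 and 38 at q = 0.5, none at q = 1. Footnote (u) can also remove non-converters with a CMFV in the last 3 months; their number cannot be derived from the documents.

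**5. EQ-5D and SF-36.** The event-status analysis in SAP 9.13 needs converters' values at the event. With no 6-month collection, these come mainly from the CMFV. If the exclusion sentence in 9.9.9 also governs 9.13, the two conflict, and the by-visit MMRM has essentially only EoS/EW data. The single-item tables for EQ-5D, SF-36 and NPI-Q stand in 9.9.9 itself, so the exclusion applies to them directly.

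**The case against.** The case on the other side has four parts, and much of it stands.

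- **Converters are not bound to be missing.** Footnote (b) permits omission but does not order it. Protocol 9.1.15.2 lists CDR and NPI-Q at EoS/EW without exception. SAP 9.9.4 lets EoS/EW data contribute to determining events, and such values were collected before confirmation. A reader might infer that every converter drops out; the documents do not support that, and the counts are upper bounds. But leaving collection to the site is not a missing-data rule.
- **Quality of life is different.** A reader might infer that EQ-5D and SF-36 are likewise analysed only at EoS/EW. SAP 9.13 plans a by-visit model and an analysis at the time of the event, and does not say whether the 9.9.9 exclusion reaches it. What remains is an unresolved conflict, plus the single-item tables.
- **The direction of bias is shown only for CDR.** It is tempting to say that NPI-Q and quality of life are also pulled toward no difference. The documents give no expected difference between converters and non-converters on these, and the MCI criteria include preserved functional independence.
- **The consequences are limited.** These outcomes lie outside the testing hierarchy (SAP 9.9.8), and CDR has no planned between-arm test. The difference in conversion is the primary endpoint, is compared again by chi-squared test in SAP 9.9.9, and CDR domain scores at diagnosis are listed. The stronger reading, that the treatment difference is lost or the primary result contradicted, does not follow.

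**Conclusion.** The point holds for CDR and NPI-Q. As written, the plan can omit many confirmed converters from the final CDR shift tables, CDR-SB summaries and NPI-Q ANCOVA although their CMFV values are in the database. The CDR tables would under-count 0-to-0.5 shifts, and more so on placebo if the assumed effect is real. For NPI-Q the selection is present but its direction is unknown. For EQ-5D and SF-36 the defect is a possible conflict between SAP 9.9.9 and 9.13, together with the single-item tables.

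The ceiling of about 126 placebo and 76 pioglitazone converters rests on the design event rates, exponential times, 12% annual dropout, equal follow-up in both arms and no EoS/EW capture in converters. The true number could be well below it. This should be corrected before unblinding.

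**What to change.** 1. In SAP 9.9.9, define the EoS/EW analysis value for CDR and NPI-Q, and for the EQ-5D and SF-36 items, as the EoS/EW visit value or, where that was not collected under Appendix A footnote (b) or (u), the last CMFV value.
2. Exempt these instruments from the exclusion of unscheduled values.
3. State that this exclusion does not apply to the quality-of-life analyses in SAP 9.13.

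The cost is SAP wording and a small programming change. The data are already collected, so no visit or assessment is added.

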This analysis could demonstrate the value of the MCI biomarker risk algorithm over a doctor using age only to assess risk for cognitively normal patients.
 - Use Age and APOE as follows:
 - High-risk: Age ≥ 76 years or carriage of the APOE $\epsilon 4$ allele.
 - Low-risk: Age less than 76 years and non-carriage of APOE $\epsilon 4$ allele.
- b. Time-to-event analyses using alternative forms of the biomarker risk algorithm variables as follows:
 - Age (continuous).

- APOE risk-status (Low, High – where High denotes carriage of at least one APOE ϵ 4 allele).
- TOMM40 ‘523 risk status (Low, Indeterminate, High – where Low corresponds to VL/VL; Indeterminate corresponds to S/VL, S/S, S/L; and High corresponds to L/VL or L/L).

The following sets of the above variables will be added to the primary biomarker comparison CPH model described in Section 9.9.3 so that assessment of the contribution of each variable to assigning a risk category relative to the biomarker risk algorithm risk classification can be made.

- Age.
- APOE risk status.
- TOMM40 ‘523 risk status.
- Age, APOE risk status.
- Age, TOMM40 ‘523 risk status.
- APOE risk status, TOMM40 ‘523 risk status.
- Age, APOE risk status, TOMM40 ‘523 risk status.

Analysis of Key Secondary Endpoints and Additional Variables in Placebo Subjects

The summaries and analyses described for the key secondary endpoints and additional continuous variables (at the domain and composite score levels only) (Section 9.9.6 and Section 9.9.9.) will also be performed using high and low risk placebo groups. The summaries will be presented by high and low risk placebo groups. The analyses will include the risk factor as a fixed factor (high vs. low risk). Other covariates (age, baseline, pooled center, gender and years of education) will be included.

9.10 Analyses of Columbia-Suicide Severity Rating Scale (C-SSRS)

The following summaries will be presented for C-SSRS scale:

- Descriptive statistics by study visit.
- Number of subjects with positive reports at baseline and during treatment.
- A shift-table to demonstrate changes from baseline in C-SSRS scores during treatment.

A subject will be summarized as having a positive report at baseline if the subject reported any of the following suicidal ideation or behavior:

- Active suicidal ideation with some intent to act, without specific plan.
- Active suicidal ideation with specific plan and intent.
- Any actual suicide attempt.

- Any interrupted suicide attempt.
- Any aborted suicide attempt.
- Any preparatory acts or behavior.

A subject will be summarized as having a positive report during treatment if the subject reported any of the following suicidal ideation or behavior:

- Active suicidal ideation with some intent to act, without specific plan.
- Active suicidal ideation with specific plan and intent.
- Any actual suicide attempt.
- Any interrupted suicide attempt.
- Any aborted suicide attempt.
- Any preparatory acts or behavior.
- Completed suicide.

